## LIST OF ABBREVIATIONS AND DEFINITION OF TERMS

|            |  |
|------------|--|
| AD         | Atopic dermatitis  |
| ADA        | Anti-Drug Antibodies   |
| AE         | Adverse event  |
| AESI       | Adverse event of special interest                              |
| ALT (SGOT) | Alanine aminotransferase                                       |
| ANCOVA     | Analysis of covariance   |
| AST (SGPT) | Aspartate aminotransferase                                     |
| BUN        | Blood urea nitrogen  |
| CRF        | Case report form   |
| EEsAI      | Eosinophilic Esophagitis Activity Index                        |
| EndoFLIP   | Endolumenal functional lumen imaging probe                     |
| EoE        | Eosinophilic esophagitis                                       |
| EoE-EREFS  | Eosinophilic Esophagitis- Endoscopic Reference Score    |
| EoEHSS     | Eosinophilic Esophagitis Histology Scoring System              |
| EoE-QOL-A  | Adult Eosinophilic Esophagitis Quality of Life (questionnaire) |
| ECG        | Electrocardiogram  |
| EOS        | End of study EOT   |
|            | End of treatment   |
| ET         | Early termination  |
| FAS        | Full analysis set  |
| HLT        | High Level Term  |
| ICF        | Informed consent form  |
| ICH        | International conference on harmonization                      |
| LDH        | Lactate dehydrogenase  |
| LOCF       | Last observation carried forward                               |
| MedDRA     | Medical Dictionary for Regulatory Activities                   |
| MI         | Multiple imputation  |
| MMRM       | Mixed effect model with repeated measures                      |
| PCSV       | Potentially clinically significant value                       |
| PD         | Pharmacodynamics   |
| PK         | Pharmacokinetic  |
| PKAS       | Pharmacokinetic analysis set                                   |
| PPS        | Per protocol set   |
| PT         | Preferred term   |

---

|           |   |
|-----------|---|
| qw        | Weekly                                    |
| RBC       | Red blood cell                            |
| Regeneron | Regeneron Pharmaceuticals, Inc.           |
| SAE       | Serious adverse event                     |
| SAF       | Safety analysis set                       |
| SAP       | Statistical analysis plan                 |
| SAS       | Statistical analysis software             |
| SC        | Subcutaneous                              |
| SD        | Standard deviation                        |
| SDI       | Straumann Dysphagia Instrument            |
| SOC       | System organ class                        |
| TEAE      | Treatment emergent adverse event          |
| WHODD     | World health organization drug dictionary |

## 1. OVERVIEW

The purpose of the statistical analysis plan (SAP) is to ensure the credibility of the study results by pre-specifying statistical approaches for the analysis of this study. The SAP is intended to be a comprehensive and detailed description of strategy and statistical techniques to be used to realize the analysis of data for R668-EE-1324 study.

This plan may be revised during the study to accommodate protocol amendments and to adapt to unexpected issues in study execution or data that affect planned analyses. The plan will be based on blinded data and will be finalized prior to the database lock.

### 1.1. Background and Rationale

Eosinophilic esophagitis (EoE) is an emerging, chronic, immune-/antigen-mediated disease characterized by esophageal dysfunction and eosinophil inflammation in the esophagus (Liacouras 2011, Weinbrand-Goichberg 2013, Zhang 2013). Adult patients with EoE have substantially impaired quality of life (QOL) due to dysphagia and the possible risk of food impaction (DeBrosse 2011, Falk 2014, Straumann 2008, Straumann 2003). Emergency endoscopy for prolonged food impactions is associated with a risk of severe esophageal injury. The prevalence of EoE in the general population was reported to range from 0.5 to 1 case per 100,000 persons (Dellon 2014a).

The pathogenesis of EoE is still unclear, however, growing evidence suggests that type 2 helper T cell (Th2)-mediated immune response plays an important role in the pathogenesis of EoE. Mutations in downstream Th2 functional genes including eotaxin-3 (chemokine [C-C motif] ligand [CCL26]), thymic and stromal lymphopoeitin (TSLP), and filaggrin (FLG) have been associated with EoE risk. Impaired barrier function of the esophageal epithelium is also thought to play a role in EoE pathogenesis. The data suggest that Th2 cytokines may be driving not only an inflammatory response, but also epithelial barrier dysfunction in the esophagus.

Consistent with the Th2-mediated inflammation observed in esophageal tissue, patients with EoE have high rates of comorbid Type 2 immune diseases, especially food allergies, atopic dermatitis (AD), asthma, and allergic rhinitis. The inflammatory damage to the esophageal epithelium results in symptoms of esophageal dysfunction, such as dysphagia. Chronic inflammation of the esophagus may also lead to remodeling, stricture formation, and fibrosis.

Current therapeutic approaches include chronic dietary elimination, swallowed topical formulation corticosteroids (not approved for the treatment of EoE in the US), and esophageal dilation. Although swallowed topical corticosteroids have been reported in clinical trials to induce partial clinical responses and histologic remission, they are not uniformly effective and can be associated with fungal infections as well as disease recurrence after discontinuation. There are currently no approved drug therapies for EoE.

Dupilumab is a human monoclonal antibody that targets the IL-4 receptor alpha subunit (IL-4R $\alpha$ ), a component of IL-4 receptors Type I and Type II, as well as the IL-13 receptor system. The binding of dupilumab to IL-4R $\alpha$  results in blockade of the function of both IL-4 and IL-13 signal transduction. Dupilumab has demonstrated preliminary efficacy in 3 other Type 2/Th2 immune diseases: asthma, chronic sinusitis with nasal polyps, and moderate-to-severe

atopic dermatitis. Because IL-4 and IL-13 are likely key pathomechanisms in EoE, dupilumab treatment may improve inflammation and clinical symptoms.

This is a multicenter, randomized, double-blind, placebo-controlled, 2-arm, parallel-group, proof-of-concept study. This study will evaluate the effect of dupilumab on relieving EoE clinical symptoms and reducing esophageal inflammation in adults. Efficacy in this study will be assessed based on clinical signs and symptoms using the EoE-specific PROs currently in development, as well as on anatomical and histological findings from endoscopy with esophageal biopsies. The placebo control will provide a reliable reference for any apparent effects of the study treatment with active IL-4R $\alpha$  inhibition. Repeat SC dose regimens as high as 300 mg qw (with or without a loading dose) for up to 16 weeks have previously been studied in phase 1, 2 and phase 3 clinical trials in healthy subjects as well as in patients with AD or asthma and were well tolerated. Therefore, a SC 600 mg loading dose followed by the repeat SC 300 mg qw dose, the highest SC repeat dose studied to date, was selected for this study.

## **1.2. Study Objectives**

### **1.2.1. Primary Objective**

The primary objective of the study is to assess the clinical efficacy of repeat SC doses of dupilumab, compared with placebo, to relieve symptoms in adult patients with active, moderate to severe EoE.

### **1.2.2. Secondary Objectives**

The secondary objectives of the study are:

- To assess the safety, tolerability, and immunogenicity of SC doses of dupilumab in adult patients with active, moderate to severe EoE
- To assess the effect of dupilumab on esophageal eosinophilic infiltration
- To evaluate the PK of dupilumab in adult patients with EoE

### **1.2.3. Exploratory Objective**

The exploratory objective of the study is to assess the effect of dupilumab on other esophageal biopsy pathologic features associated with EoE, as well as esophageal distensibility, which is reduced in EoE patients.

## **1.3. Modifications from the Statistical Plan in the Final Protocol**

NA

## **1.4. Modifications from the Previously Approved SAP**

NA

## 2. INVESTIGATIONAL PLAN

### 2.1. Study Design and Randomization

This is a phase 2, multicenter, double-blind, randomized, placebo-controlled study investigating the efficacy, safety, tolerability, PK, and immunogenicity of dupilumab in adult patients with EoE. Patients will be randomized in a 1:1 ratio to receive SC 600 mg dupilumab or SC placebo loading dose followed by weekly SC 300 mg dupilumab or SC placebo during the 12-week double-blind treatment phase. The randomization will be stratified by baseline Straumann Dysphagia Instrument (SDI) PRO score ( $\geq 5$  and  $\leq 7$  versus  $> 7$ ).

### 2.2. Sample Size and Power Considerations

The sample size calculations are based on the change from baseline in SDI score to week 12. The study of Straumann 2010 has a 2-week treatment period and the 3-point improvement from baseline is observed at end of week 2. A 3-point improvement from baseline is assumed for the study at both week 10 and week 12, so the power calculation for change from baseline in SDI score to week 12 is the same as the one at week 10. In the Straumann adult study, change from baseline in SDI score for active and placebo treatment group are -3.39 (2.46) [mean (maximum possible SD)] and -0.61 (2.19) [mean (maximum possible SD)] respectively.

A sample size of 18 patients per treatment arm will provide 94% power to detect a treatment effect, with an expected mean difference of 3 points in change from baseline to week 12 in SDI score between dupilumab and placebo at a 2-sided t-test with 5% significance level and an assumed SD of 2.46. Taking into account the assumed 15% dropouts, 22 patients per treatment arm will be enrolled.

### 2.3. Study Plan

The study will consist of 3 periods: screening, 12 week double-blind treatment, double-blind follow-up:

| Screening              | Treatment Period (Weeks) a,b |   |   |   |                |                |                |   |                |                 |                 | Follow-up c |                  |
|------------------------|---|---|---|---|----------------|----------------|----------------|---|----------------|-----------------|-----------------|------------------------|------------------|
|                        | 1                                       | 2 | 3 | 4 | 5 d | 6 d | 7 d | 8 | 9 d | 10 d | 11 d | EOT
(Week 12)       | EOS
(Week 28) |
| B/R
(Day -35 to -1) | (Day 1)                                 |   |   |   |                |                |                |   |                |                 |                 |                        |                  |

B/R = baseline/randomization; EOT = end of treatment; EOS = end of study.

Note: The scale is not linear.

a Patients will receive a weekly injection of study drug from day 1 through week 12 (with the last dose at week 11).

b Patients will be monitored at the study site for 30 minutes after each of the first 5 doses (visits 2 to 6) of study drug.

c Follow-up visits will occur every 4 weeks.

d Weeks 5, 6, 7, 9, 10, and 11 will be telephone visits.

After providing informed consent, patient eligibility will be assessed at the screening visit (to occur between day -35 and day -1). Patients who meet eligibility criteria will undergo day 1 baseline assessments. Patients will be randomized in a 1:1 ratio to receive dupilumab or placebo

during the 12-week double-blind treatment phase. After the 12-week double-blind treatment phase, patients will be followed off-study drug for an additional 16 weeks.

Patients may receive concomitant medications (except for prohibited medications) as needed, at the discretion of the investigator, while continuing study treatment. Frequency of use and type of product will be documented. If medically necessary, rescue medications or emergency esophageal dilation may be provided to study patients. Patients receiving rescue therapy will be discontinued from study treatment. These patients will remain blinded and will be asked to return to the clinic for all remaining study treatment visits and participate in all follow-up assessments according to the visit schedule.

Efficacy, safety, and laboratory assessments will be performed at specified time points throughout the study. Samples for the assessments of dupilumab concentration and assessment of anti-drug antibody (ADA) response to dupilumab, as well as research samples will be collected at specified time points throughout the study. In response to AE's of special interest like anaphylaxis or hypersensitivity additional samples closer to the event may be collected and analyzed for ADA, based on the judgement of the medical investigator and/or medical monitor.

The end of the double-blind treatment period visit occurs at week 12, 1 week after the last dose of study drug. The maximum duration of the double-blind study is approximately 33 weeks including screening and follow-up.

### **3. ANALYSIS POPULATIONS**

In accordance with guidance from the International Conference of Harmonization of Technical Requirements for Registration of Pharmaceuticals for Human Use (ICH) guideline [ICH E9 Statistical Principles for Clinical Trials \(1998\)](#), the following populations of analysis will be used for all statistical analyses.

#### **3.1. The Full Analysis Set (FAS)**

The full analysis set (FAS) includes all randomized patients. Efficacy analyses will be based on the treatment allocated by the IVRS/IWRS at randomization (as randomized). This is the primary analysis population for efficacy analyses.

#### **3.2. Per Protocol Analysis Set (PPS)**

The per protocol analysis set (PPS) includes all patients in the FAS except for those who are excluded from this analysis because of major efficacy-related protocol violations.

A major efficacy-related protocol violation is one that may affect the interpretation of study efficacy results. The criteria of major efficacy-related protocol deviation are defined as following:

- Any major violations of efficacy-related entry criteria
  - Inclusion criteria 2, 3, 5
  - Exclusion criteria 8, 12
- Patients who received <80% of the scheduled doses during the double blind treatment period

Final determination of the PPS will be made in the blinded manner prior to the database lock.

#### **3.3. The Safety Analysis Set (SAF)**

The safety analysis set (SAF) includes all randomized patients who receive any study drug, and will be analyzed as treated.

The actual treatment group as treated is defined by the following rules:

- For a patient randomized to dupilumab,
  - if the patient received all placebo injections, the actual treatment will be assigned as placebo
  - if the patient received at least one dupilumab injection, the actual treatment will be assigned as dupilumab
- For a patient randomized to placebo,
  - if the patient accidentally received one or more dupilumab injections, the actual treatment will be assigned as dupilumab; otherwise it will remain as placebo

The safety analyses will be based on the SAF.

For safety summaries, three analysis periods are defined as follows:

- Week 12 treatment period is defined as Day 1 from start of administration of the first dose of study drug through week 12 of the double-blind period (85 days starting from the first dose of study drug if the date of week 12 treatment visit is unavailable).
- Follow-up period is defined as from week 12 of the double-blind period to the last visit of the double-blind period.
- Overall study Period is defined as day 1 to the date of the end of study visit, consisting of both the treatment and follow-up periods

### **3.4. The Pharmacokinetic Analysis Set (PKAS)**

The PK analysis set includes all randomized patients who received any study drug and who had at least one non-missing PK sample result following the first dose of study drug, and will be analyzed as the treated groups defined in the SAF.

### **3.5. The ADA Analysis Set (AAS)**

The ADA analysis set includes all treated patients who received any study drug and had at least 1 non-missing ADA result in the ADA assay following the first dose of the study drug.

### **3.6. Subgroups**

Subgroups are defined by key baseline factors recorded on the CRF and listed as follows

Subgroups to be considered for efficacy/safety analyses:

- Age group ( $\geq 18$ - $<40$ ,  $\geq 40$ - $<65$ ,  $\geq 65$ )
- Sex (Male, Female)
- Baseline weight group ( $<70$  kg,  $\geq 70$ - $<100$  kg,  $\geq 100$  kg)

93% patients enrolled for this study are white so no subgroup for ethnicity or race as all patients are not Hispanic or Latino

## 4. ANALYSIS VARIABLES

### 4.1. Demographic and Baseline Characteristics

The following demographic and Baseline characteristics variables will be summarized:

- Demographic variables: Age at screening with grouping (year;  $\geq 18$ - $<40$ ,  $\geq 40$ - $<65$ ,  $\geq 65$ ), Sex, Ethnicity with grouping (Hispanic or Latino, Not-Hispanic or Latino), Race with grouping (White, Black, Asian, Other), Baseline weight with grouping (kg,  $<70$ ;  $\geq 70$ - $<100$ ,  $\geq 100$ ), Height (m), and BMI ( $\text{kg}/\text{m}^2$ ;  $<15$ ,  $\geq 15$ - $<25$ ,  $\geq 25$ - $<30$ ,  $\geq 30$ ),
- Baseline characteristics: Age at EOE diagnosis, Duration of EoE, age at first esophageal dilation, number of documented dysphagia episodes, SDI PRO score, EEsAI PRO score, EoE-QOL-A PRO score, EoE-EREFs, distensibility plateau, peak eosinophils/hpf, EoEHSS stage, EoEHSS grade, allergic disease, peripheral eosinophil counts, serum total Immunoglobulin E (IgE).

### 4.2. Medical History and EoE Disease Medical History

Medical history will be coded to a Preferred Term (PT) and associated primary System Organ Class (SOC) according to MedDRA version 19.1 at the coding of CRO. Information on conditions related to EoE includes diagnosis of EoE and EoE treatment history.

### 4.3. Pre-treatment/ Concomitant Medications and Procedures

Medications/Procedures will be recorded from the day of informed consent until the EOS visit. Medications will be coded to the ATC level 2 (therapeutic main group) and ATC level 4 (chemical/therapeutic subgroup), according to the latest available version of WHO Drug Dictionary (WHODD) version Sep 2016 at the coding of CRO. Patients will be counted once in all ATC categories linked to the medication.

Pre-treatment medications/procedures: medications taken or procedures performed prior to administration of the first study drug.

Concomitant medications/procedures: medications taken or procedures performed following the first dose of study drug through the EOS visit.

Prohibited concomitant medications/procedures during week 12 treatment period Treatment with the following concomitant medications is prohibited:

- Medications used for the treatment of EoE .
- Allergen immunotherapy.
- Patients who are not using PPI in the 8 weeks prior to screening cannot start PPI therapy prior to EOT visit
- Treatment with a live (attenuated) vaccine
- Treatment with an investigational drug (other than dupilumab)

Treatment with the following concomitant procedures is prohibited:

- Major elective surgical procedures
- Esophageal dilation (considered rescue procedure)
- Diet change.

If medically necessary (eg, for treatment of intolerable EoE symptoms) patients may be rescued with a prohibited medication or procedure at the discretion of the investigator. Patients who receive rescue treatment with a prohibited medication or procedure through week 12 will be permanently discontinued from study drug.

Rescue treatments for EoE: Blinded adjudication of rescue treatments will be implemented before database locks by considering the type of medications. A predetermined algorithm for rescue medications listed in [Appendix 10.6](#) will be used to programmatically search the concomitant medications (CMs). The rescue CMs will be reviewed and adjudicated by the medical monitor in a blinded fashion.

All patients will complete the schedule of study visits and assessments whether or not they complete study treatment. Investigators should make every attempt to conduct efficacy and safety assessments immediately before administering any rescue treatment. An unscheduled visit may be used for this purpose if necessary.

## **4.4. Efficacy Variables**

Due to failure with electronic diaries, data from many patients are missing for the week 12 analysis. Week 10 timepoint is therefore chosen as endpoints for SDI and EEsAI in a blinded fashion prior to database lock to increase available data for analysis. Week 12 remains the endpoints for other efficacy endpoints.

### **4.4.1. Primary Efficacy Variables**

The primary efficacy endpoint is the change in the Straumann Dysphagia Instrument (SDI) patient reported outcome (PRO) score from baseline to week 10.

#### Straumann Dysphagia Instrument (SDI)

The SDI is a PRO that has been used in clinical studies to determine the frequency and intensity of dysphagia. The SDI has a 1-week recall period. Frequency of dysphagia events is graded on a 5-point scale: 0 = none, 1 = once per week, 2 = several times per week, 3 = once per day, and 4 = several times per day, and intensity of dysphagia events is graded on a 6-point scale: 0 = swallowing unrestricted, 1 = slight sensation of resistance, 2 = slight retching with delayed passage, 3 = short period of obstruction necessitating intervention (eg, drinking, breathing), 4 = longer-lasting period obstruction only removable by vomiting, and 5 = long-lasting complete obstruction requiring endoscopic intervention. The SDI total score is the sum of scores of frequency of dysphagia and intensity of dysphagia, and ranges from 0 to 9. In the Straumann adult study of swallowed budesonide TCS (Straumann, Gastroenterology 2010), a clinical response (improvement) was defined as a decrease in SDI score of at least 3 points from baseline. SDI score is the sum of scores of frequency of dysphagia and intensity of dysphagia. SDI score will be set to missing if score of frequency of dysphagia or score of

intensity of dysphagia is missing. If intensity of dysphagia event is greater than 0 and frequency of dysphagia is 0, then frequency of dysphagia will be set to 1.

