#### Eosinophilic Esophagitis Activity Index (EEsAI) PRO

The EEsAI is a multimodular index in development at University Hospital Inselspital (Berne, Switzerland), a part of the international EEsAI study group. The EEsAI PRO module (questionnaire) used in this study includes items related to the intensity and frequency of dysphagia, and the influence of specific food groups on dysphagia symptoms. The PRO instrument contains 5 domains addressing symptoms while eating or drinking includes items on duration, frequency, and severity of dysphagia, time required for meal intake, dysphagia upon consuming liquids, and pain when swallowing. The visual dysphagia question (VDQ) addresses the severity of dysphagia when consuming food of 8 distinct consistencies. The 8 food consistencies and examples of foods to illustrate those consistencies are: (1) solid meat (such as steak, chicken, turkey, and lamb), (2) soft foods (such as pudding, jelly, and apple sauce), (3) dry rice or sticky Asian rice, (4) ground meat (hamburger and meatloaf), (5) fresh white untoasted bread or similar foods (such as doughnuts, muffins, and cake), (6) grits, porridge (oatmeal), or rice pudding, (7) raw fibrous foods (such as apples, carrots, and celery), and (8) French fries. The

behavioral adaptations (avoidance, modification, and slow eating [AMS] of various foods) are assessed in the context of consuming 8 distinct food consistencies. The total EEsAI PRO score ranges from 0 to 100. The details of the calculation are provided in [Appendix 10.5](#). The EEsAI PRO utilizes 24-hour and 1-week recall periods. Patients will electronically complete this questionnaire daily and weekly from the beginning of screening through end of study or early termination. EEsAI score will be set to missing if one of 5 domain scores is missing.

Derived weekly EEsAI score will be produced by average daily EEsAI score for each patient and calculated as the prorated average of the daily EEsAI score. For example, if there are 4 daily EEsAI score in a week, the prorated average = (score1 + score2 + score3 + score4)/4. A minimum of 4 days nonmissing daily score in a week is required to calculate the derived weekly score. If there are <4 days of daily score, the derived weekly score will be missing. Derived weekly EEsAI score will cover the same time period as the weekly EEsAI score.

Details for calculation EEsAI score can be found in [Appendix 10.5](#).

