## 10. APPENDIX

### 10.1. Summary of Statistical Analyses

#### Efficacy Analysis:

| Endpoint   | Analysis Population | Primary Statistical Method                              | Supportive/Sensitive Statistical Method   | Subgroup Analysis | Other Analyses |
|--|---------------------|---|---|-------------------|----------------|
| Change in the SDI score at week 10 from baseline | FAS                 | MI + ANCOVA   | MI+ANCOVA regardless of rescue, ANCOVA on LOCF, WOCF and OC, and primary efficacy analysis on PPS | Yes               | Line plot      |
| Secondary continuous variables                   | FAS                 | MI + ANCOVA   | NO  | No                | Line plot      |
| Categorical variables                            | FAS                 | Fisher exact test / define missing as treatment failure |   | No                | Histogram      |
|  |                     |   |   |                   |                |

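### The SDI scoring rule discards a recorded frequency of none when only the intensity item is blank; any such record is imputed in the primary analysis and counted as failure in the responder analysis

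*SAP*

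**What the plan says.** - **SDI scoring (SAP 4.4.1).** The total is the sum of a frequency item (0 to 4, where 0 is none) and an intensity item (0 to 5, where 0 is unrestricted swallowing). The missing-item rule reads "SDI score will be set to missing if score of frequency of dysphagia or score of" intensity is missing. The only rule that links the two items is "If intensity of dysphagia event is greater than 0 and frequency of dysphagia is 0, then frequency of dysphagia will be set to 1".
- **Primary analysis (SAP 5.7.2).** Missing SDI values in the FAS are imputed 50 times. The imputation model contains treatment, baseline SDI and the observed values up to week 10.
- **Sensitivity analyses (SAP 5.7.2).** These are MI regardless of rescue, LOCF, WOCF and an observed-case ANCOVA.
- **Responder endpoint (SAP 4.4.2).** Response is a fall of at least 3 SDI points at week 10. Appendix 10.1 tells the analyst to "define missing as treatment failure" for categorical variables. Section 5.7.3 names only early withdrawal and rescue as non-response.
- **EEsAI (SAP 4.4.2).** "EEsAI score will be set to missing if one of 5 domain scores is missing".

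**The concern.** The intensity item grades dysphagia events. A patient who reports none has no event to grade and could leave the item blank. The rule then discards the frequency answer as well, even though a total of 0 is the natural reading of what was recorded.

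The SAP is willing to repair items logically, but its one repair can only raise a score. The mirror case, where the recorded answer points to the best possible score, goes to the missing-data rule.

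This pattern requires a frequency answer of 0, so the missingness would be related to a good outcome. Multiple imputation that assumes missing at random does not address that. If the drug works, the pattern would be expected more often on dupilumab, and the bias would then run against it. Section 4.4 reports that diary failure has already cost many patients their week 12 data, so a value that can be recovered at week 10 is worth keeping.

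**Working it through.** **1. The plan's own figure.** Section 2.2 states "A sample size of 18 patients per treatment arm will provide 94% power to detect a treatment effect". Its inputs are a 3-point difference between the arms, an SD of 2.46 and a two-sided test at the 5% level. The noncentrality is 3 / (2.46 × √(2/18)) = 3 / 0.82 = 3.66 on 34 df, which gives power 0.944. The 94% reproduces. Enrolment is 18 / 0.85 = 21.2, rounded up to 22 per arm. The scoring question does not change these planning figures.

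**2. One affected record under each analysis.** The strata in section 2.1 start at SDI 5, so baseline is taken as at least 5. Suppose frequency is 0 and intensity is blank at week 10.

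| Analysis | Under the SAP as written | If scored 0 |
|---|---|---|
| Primary, MI + ANCOVA | imputed | change of -5 or better |
| MI regardless of rescue | imputed | change of -5 or better |
| LOCF | earlier score carried forward | change of -5 or better |
| WOCF | worst post-baseline score | change of -5 or better |
| Observed case | patient left out | change of -5 or better |
| Responder (Appendix 10.1) | failure | responder (threshold -3) |

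No planned analysis uses the recorded frequency answer.

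**3. Shift per patient, as an illustration.** Take imputation at the active-arm mean of -3.39, which section 2.2 cites from a 2-week study of another drug.
- Baseline 5: 5 - 3.39 = 1.61 points.
- Baseline 6: 6 - 3.39 = 2.61 points.
- Two such patients of 22: 1.61 × 2/22 = 0.15 and 2.61 × 2/22 = 0.24 points on the arm mean.

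The imputation also uses the patient's own earlier scores. Assume the previous SDI was also 0, SDs are equal, and the within-patient correlation ρ is 0.5 to 0.9. The loss is then (1 - ρ) times the figures above:
- smallest: 0.1 × 1.61 = 0.16 points;
- largest: 0.5 × 2.61 = 1.3 points;
- two patients of 22: about 0.01 to 0.12 points on the arm mean.

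**4. Effect on the contrast, less favourable case.** Assume 18 per arm, a placebo change of -0.61, a dupilumab change of -3.61, baseline 6 and SD unchanged. Let k dupilumab patients with a true score of 0 be imputed at the mean of the rest of their arm. That mean is (18 × (-3.61) + 6k) / (18 - k).

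| k | Mean of the rest | Difference | Power |
|---|---|---|---|
| 0 | -3.61 | 3.00 | 0.94 |
| 1 | -3.47 | 2.86 | 0.92 |
| 2 | -3.31 | 2.70 | 0.89 |
| 3 | -3.13 | 2.52 | 0.85 |

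For k = 3 and a baseline of 5 to 7, the difference runs from 2.72 to 2.32 and power from 0.90 to 0.79.

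**5. Responders.** A normal model with the same means and SD gives response probabilities of Φ(0.61/2.46) = 0.60 and Φ(-2.39/2.46) = 0.17. That is about 13 and 4 of 22. Each true responder coded as failure costs 1/22 = 4.5 percentage points.

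| Dupilumab v placebo | Fisher p |
|---|---|
| 13 v 4 | 0.012 |
| 12 v 4 | 0.027 |
| 11 v 4 | 0.055 |
| 10 v 4 | 0.10 |

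The value of k is an assumption throughout. With k = 0 there is no effect.

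**The case against.** **The pattern may never occur.** Intensity has its own zero answer, so a symptom-free patient has something to tick. The cross-item rule implies that intensity is collected even when frequency is 0. The missing data that the SAP reports come from diary failure, not skipped items, and a diary that forces both items would bring the count to zero. This stands and makes the point conditional. It does not remove it, because the SAP writes a rule for a missing item and does not say that the diary prevents one.

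**Frequency 0 is not proof of a dysphagia-free week.** A reader might infer that intensity is then known to be 0. The SAP does not support that: when intensity is above 0, it overrides the frequency answer. Scoring the blank as 0 is therefore a convention that rests on one item. It is still the reading that fits the only answer given.

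**The patient is not lost from the primary analysis.** A reader might infer that the best outcomes are dropped. They are imputed, and the patient stays in the FAS. Only the observed-case sensitivity analysis leaves the patient out.

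**Requiring both items of a two-item sum is conventional and blind to treatment.** That is true, and the responder endpoints are secondary, without multiplicity adjustment, in a proof-of-concept study. The stakes are modest, but so is the cost of the change.

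**Conclusion.** The point holds as a conditional gap in the SDI scoring rule. Read literally, section 4.4.1 discards a recorded frequency of none when only intensity is blank. The total is then imputed in the primary analysis and, under Appendix 10.1, counted as failure in the responder analysis. A patient with a baseline of at least 5 and a score of 0 would be a responder. Any resulting bias runs against the arm where the pattern is more common.

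The size is unknown and may be zero. The 1.6 to 2.6 points per patient rest on imputation at the arm mean. A reader might take them as a minimum, but they are not one: where earlier visits predict week 10 well, the loss falls to a few tenths of a point. The responder effect is firmer, since each affected patient moves from responder to failure.

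A reader might also infer that the EEsAI has the same defect. The SAP does not show it. The duration item has a zero category (5 minutes or less), and nothing indicates that it is left blank after an answer of never. That question needs only a check.

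**What to change.** Under blind and before the first database lock:

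1. Add to section 4.4.1: *If frequency = 0 and intensity is missing, intensity is set to 0 and the SDI total is 0.* Keep the missing rule for every other pattern. Apply the sentence before imputation and before responder status is derived.
2. Report the blinded count of affected records. If the diary forces both items, say so; the count is then zero and the sentence has no effect.
3. Align section 5.7.3 with Appendix 10.1 on how a missing week 10 responder value is handled.
4. For the EEsAI, check under blind whether duration can be blank after an answer of never. Set the duration domain to 0 only if it can.

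The cost is one sentence and about one line of derivation code for the SDI, plus a blinded data check. The small downside is reliance on a single item, one that the SAP itself overrides when intensity is above 0.
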